1. BACKGROUND INFORMATION AND STUDY RATIONALE

1.1 Background

Chronic pain, defined by the International Association of Pain (IASP) as pain persisting or recurring for more than three months, refers to a complex and heterogeneous group of disorders that produce significant disability and emotional distress.¹⁻⁵ Studies suggest that chronic pain affects at least 10% of the worldwide population, with estimates approaching 20–25% in some regions⁶.

According to IASP⁷, chronic pain is the “parent code” for 7 other codes that comprise the most common clinically relevant groups of chronic pain conditions (Top-level diagnosis): (1) chronic primary pain; (2) chronic cancer-related pain; (3) chronic post-surgical or post-traumatic pain; (4) chronic neuropathic pain; (5) chronic secondary headache or orofacial pain; (6) chronic secondary visceral pain; and (7) chronic secondary musculoskeletal pain. Within the primary pain syndrome, pain is conceived as a disease or health condition, whereas in secondary pain syndromes, pain is regarded as a symptom.

Given the limited access to physical and psychological interventions for chronic pain⁷⁻⁹ and the variable efficacy and tolerability of currently available medications^{10,11}, there is a growing interest in the use of cannabinoids (medical cannabis and cannabis-based medicines) for chronic pain management. The legalization of cannabis in at least 14 countries and regulatory approval of cannabis extract preparations, as well as the emergence of synthetic cannabinoids and analogs, is expected to herald an increase in the number of individuals seeking cannabinoids as a means of pain relief. A recent European Pain Federation position paper provided a series of recommendations surrounding cannabis-based medicines to this effect¹².

Cannabis has a long history of therapeutic use for pain and other indications. Research into the pharmacology of cannabinoids and their mechanisms of action¹³ has led to the identification of an endocannabinoid system (ECS) in humans, composed of endogenous cannabinoids, the proteins responsible for their synthesis, release and degradation, their associated metabolites, and cannabinoid receptors¹⁴. Of more than 120 cannabis-derived phytocannabinoids, the majority of cannabis’ effects are attributed to two compounds: delta-9-tetrahydrocannabinol (THC), the main psychoactive cannabinoid in cannabis, and cannabidiol (CBD), a non-euphoric cannabinoid that has been investigated in pre-clinical studies for effects on anxiety, cognition, inflammation, and pain^{15,16}. Both THC and CBD have been demonstrated to bind and modulate various receptors within the ECS to mediate their proposed therapeutic effects.

Despite accumulating experimental and clinical evidence both for and against the use of cannabis products in subjects with chronic pain, there are limited guidelines or standards of care to facilitate the safe and effective prescription of cannabinoid formulations by physicians who treat subjects with chronic pain. This study aims to establish a Spectrum Therapeutics (ST) Chronic Pain Registry that will collect descriptive, clinical, and outcome data on the use of ST medical cannabis products in subjects with chronic pain. These real-world data will provide insights regarding physician-recommended treatment regimens, titration, safety, and changes in self-reported pain relief, daily function, and quality of life. Additionally, data generated from the registry will aid in the development of further controlled clinical studies, market access initiatives, educational programs, and future publications.

1.2 Rationale

Primary chronic pain and chronic musculoskeletal pain are the most common reasons people cite for using medical cannabis products^{13,17-20}. Rapid changes in the global regulatory landscape regarding medical use of cannabis and cannabinoids have had a significant impact on health care professionals who currently receive little or no education on medical cannabis¹⁹. Appropriate knowledge about the use of medical cannabis and evidence to support the development of clinical guidelines is essential for the effective use of medical cannabis by health care professionals. This sentiment parallels requests for the development of research in this area by professionals and the media^{20,21}.

2. STUDY OBJECTIVES AND PURPOSE

2.1 Objectives

The overall scope of this research is to collect prospective real-world data on the physician-recommended use of ST products for chronic pain in countries where ST products are commercially available. This effort will yield a data generation platform to meet primary and secondary study objectives and establish a research framework for future efforts.

2.1.1 Primary Objective

- To describe patterns of physician selection of Spectrum Therapeutics (ST) medical cannabis treatment regimen expressed as average daily dose of THC and CBD (in mg), and mode of administration (ingested or inhaled) in the management of chronic non-cancer pain in countries where these products are commercially available.

2.1.2 Secondary Objectives

- To describe subject product and dose adjustment (under medical follow-up) over time.
- To assess outcomes of treatment including pain relief and effects on sleep, daily functioning, and quality of life.
- To assess global impressions of treatment effectiveness as reported by subjects and physicians.
- To assess changes in daily dose of opioids, other medications over time.

2.1.3 Safety Objective

- To assess the safety and tolerability of individual ST products in subjects with chronic pain.

3. STUDY DESIGN

3.1 Description of the Study

The present study is a prospective, observational registry designed to generate real-world data on the physician-recommended use of ST products to manage chronic pain in countries where these products are commercially available. The study will enroll up to 1500 subjects from 50-150 sites in geographic regions of ST product distribution over a two-year period. Physicians will recruit subjects during routine care visits and assess whether subjects with chronic pain are candidates for medical cannabis treatment. Once enrolled, subjects will be followed for 1 year to collect data on demographics, chronic pain classification, cannabis experience, treatment goals, concomitant medication(s), ST treatment regimen, clinical assessment, subject-reported outcomes, and safety.

The study includes five physician-verified visits (baseline, 2, 4, 8, and 12 months), and four at-home subject-verified follow-ups (months 1, 3, 6, 10). Physician verified follow ups can be conducted in person or via telemedicine. Additionally, should there be a need, according to the physician's judgement, there may be other unscheduled visits, either in-clinic, or via telemedicine. All data will be collected using *REDCap Cloud* via online eCRFs. The study time-points were selected based on the typical timeframe of titration in routine care, and adverse event (AE) emergence for the use of cannabis products in new subjects; a majority of titration occurs within the first month of taking a new cannabis product²⁹. Visits were also spaced out so that subject retention may be maximized, and treatment adjusted in a timely manner. Later time-points are designed to capture longer-term treatment-related outcomes while screening for AE emergence and medication use changes in the long term.

At the first visit (Day 1), subjects will complete the informed consent. A pregnancy test will be administered to women of childbearing potential, and the site physician or study site personnel will confirm subject eligibility criteria. Following this, the site physician or study site personnel trained in the use of *REDCap Cloud* will assist each subject in creating a *REDCap Cloud* account and completing the baseline assessment (Appendix 1). The first visit (Day 1) will assess important baseline information, including demographics, chronic pain classification, cannabis experience, concomitant medications, treatment goal, and ST treatment regimen. Subjects will complete the Brief Pain Inventory-Short Form (BPI-SF) and Euro- Quality of life Assessment (EQ5DL) at this visit.

At each subsequent physician-verified visit (a total of 4), the site physician or study site personnel will assist with the completion of physician follow-up assessment (Appendix 2) via *REDCap Cloud*, and reassess ST treatment regimen, concomitant medications, effectiveness and tolerability of the ST treatment regimen (including AEs & SAEs). Subjects will complete the BPI-SF, EQ5DL, and Patient Global Impression of Change (PGI-C) and physicians will complete the Clinical Global Impression-Improvement (CGI-I).

Four subject-verified follow-up assessments will be completed by subjects via the *REDCap Cloud* online portal (Appendix 3). Subjects will receive an automated email one week prior and the day of subject-verified follow-up with a reminder to complete the online assessment. The subject-verified online assessment will include questions about their ST treatment regimen, additional cannabis consumption, numeric rating scale (NRS) pain items of the BPI-SF, the EQ5D-5L, and the PGI-C.

Spontaneous AE reporting will be entered in *REDCap Cloud* by the subject during subject follow-up assessments, using the Subject AE log (Appendix 3). Physicians will verify and assess all AEs entered at physician follow-ups, using the Physician AE form (Appendix 2). All serious adverse events will be sent directly to Canopy Growth's Global Pharmacovigilance Department (GPVD) in real-time, where they will be reviewed with respect to country specific regulatory requirements. All non-serious adverse events will be sent in a monthly report to GPVD.

In the event of ST treatment discontinuation, or study dropout, physicians will be asked to follow-up with subjects to complete the ST Discontinuation Assessment and Exit assessment (Appendix 4). Based on physician answers to ST Discontinuation Assessment, subjects will either stay enrolled in the study (e.g., discontinue all cannabis treatment, but continue to be monitored by site physician for chronic pain), or be withdrawn (e.g., unwilling to stay in the study, switched cannabis licensed producer).

A complete schedule of events is provided in **Table 1**.

4. STUDY MEDICATION

For the purposes of this study, subjects enrolled will have been prescribed/authorized Spectrum Therapeutics products that are commercially available in participating countries. It is important to note that product availability varies from country to country. No country except Canada, has access to the full ST medical portfolio (e.g., only flowers are available in Germany).

The full repertoire of Spectrum Therapeutics products is outlined here (see Figure 1). It encompasses six “colors” (order from Red to Yellow follows the descending THC:CBD ratio), and five types of formulations: soft gels, spray*, oil, flowers and vapes). Refer to webpage for the most up to date products available per country <https://www.spectrumtherapeutics.com/canada/en/patients/products>.

Figure 1. Repertoire of Spectrum Therapeutics Products.

Cannabinoid Content for Spectrum Therapeutics Products			
Spectrum Product	Percentage of THC & CBD per gram of weight Dried flower (%)	Milligram of THC & CBD per milliliter of Oil (mg/ml)	Milligram of THC & CBD per Soft gel (mg)
Red 	(17-23) THC : (< 0.7) CBD	(26.3) THC : (<1) CBD	(2.5-10) THC : (<1) CBD
Orange 	(10-14) THC : (<1) CBD	NA	NA
Purple 	(8-11) THC : (< 0.7) CBD	NA	NA
Blue 	(6-10) THC : (8-11) CBD	(10) THC: (12-15) CBD	(2.5 – 10) THC : (1.75-15) CBD
Green 	(4-7) THC: (7-10) CBD	NA	NA
Yellow 	(<1) THC : (10-14) CBD	(<1) THC : (20) CBD	(<1) THC: (5-20) CBD

*Spray formulation is the most recent addition to the formulations and not yet featured on the web site.

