4.2 Study Medication: Cannabinoid Content Calculation

On entering study medication information into *REDCap Cloud*, the preprogrammed algorithm will calculate the intake amount of mgs of THC and CBD for all formulations, and whether it was inhaled or ingested. Only limited data exist on the plasma concentration of circulating cannabinoids and their metabolites resulting from inhalation of cannabis products. It is known that factors influencing this include, but are not limited to, pattern of smoking or vaping (length of inhalation), as well as the flower combustion temperature. It is possible that these data may be calculated in retrospect (unlike other formulations that will allow for real time mg calculation), if more structured studies are conducted to evaluate the cannabinoid intake from smoked and/or vaped products, from different flower varieties.

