7. OUTCOME ASSESSMENTS

7.1 Study Endpoints

Primary endpoints

- Physician selection of Spectrum Therapeutics (ST) medical cannabis treatment regimen and changes over time in:
 - (1) average daily dose of THC and CBD (in mg);
 - (2) route of administration (inhaled or ingested).

Secondary endpoints

- Subject selection of ST treatment regimen and changes over time in:
 - (1) average daily dose of THC and CBD (in mg);
 - (2) route of administration (inhaled or ingested).
- Change in BPI-SF responses from baseline.
- Change in EQ5D-5L responses from baseline.
- PGI-C for the target treatment goal.
- CGI-I for the target treatment goal.
- In subjects taking an opioid, changes in opioid use over time (calculated as milligram morphine equivalents [MME]/day).
- Among subjects taking other medication, total daily dose change over time.

Safety endpoint

- Incidence of AEs stratified by product and formulation.

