Benzodiazepines Dosing Information

Name of drug _____

Daily dose of [baseline_visit][benzo1_name](total mg per day) _____

Check to add additional benzodiazepine medications

Name of drug _____

Daily dose of [baseline_visit][benzo2_name] (total mg per day) _____

Check to add additional benzodiazepine medications

Name of drug _____

Daily dose of [baseline_visit][benzo3_name] (total mg per day) _____

Opioid Dosing Information

Please enter MME (total daily morphine equivalent dose in mg) _____

Other Medication Information

Please indicate name of other drugs not included in the above classes _____

Daily dose (total mg per day), if available _____

ST Regimen Canada

[figure not shown]

Please enter in the table below total daily amount of Spectrum Therapeutics products consumed. Please be conscious of the units provided:

Inhaled cannabis = total number of inhalations per day

Ingested oils = total mL per day

Spray format = total number of sprays per day

Capsules & edibles = total number of capsules or total number of chocolate bar squares per day

	Inhaled Formats (dried flower, extract vaporizers) -- report daily total number of inhalations	Ingested Oil Formats - report daily total number of mLs	Spray Formats - report daily total number of sprays	Low Potency Capsule & Edible Formats - report daily total number of low-potency capsules (i.e. 2.5 mg), number of chocolate bar squares, etc.	High Potency Capsule Formats - report daily total number of high-potency capsules
Red (examples include Spectrum #1-4; Tweed Bakerstreet, Highlands, Houdstooth, Donegal; LBS Sunset)	 inhalations  	 mL  	 sprays  	 capsules  	 capsules  
Orange	 inhalations  		 sprays  		
Purple (examples include LBS Ocean View)	 inhalations  		 sprays  		
Blue (examples include Tweed Penelope)	 inhalations  	 mL  	 sprays  	 capsules  	 capsules  
Green (examples include Tweed Argyle)	 inhalations  	 mL  	 sprays  	 capsules  	 capsules  

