Yellow (examples include Tweed CBD Softgels)	 inhalations  	 mL  	 sprays  	 capsules  	 capsules  
Spectrum Clear (or White)		 mL  			

You indicated that your patient has been recommended an inhaled format. Please identify their most common method of administration.

(inhal_admin)

[Branching logic exists]

- Smoked
- Dried flower vaporizer (e.g. Stroz and Bickel, PAX)
- Extract vaporizer (e.g. vape pen cartridge)

Do you or your patient know the temperature set point of the vaporizer (in °C)

(inhal_vape_Y/N)

[Branching logic exists]

- Yes
- No

If known, please provide the temperature set point of your patient's vaporizer (in °C) _____

(inhal_vape_temp)

(125 / 300)

[Branching logic exists]

Calculated, approximated total daily dose of THC and CBD (in mgs)

	THC	CBD
Inhaled	
(inhal_THC)
  
View Equation
	
(inhal_CBD)
  
View Equation

Ingested	
(ingest_THC)
  
View Equation
	
(ingest_CBD)
  
View Equation

Patient reported outcomes

BPI

Throughout our lives, most of us have had pain from time to time (such as minor headaches, sprains, and toothaches). Have you had pain other than these everyday kinds of pain today?

- Yes
- No

Please select the number (0= no pain, 10= pain as bad as you can imagine) that best describes your pain at its worst in the last 24 hours.

- 0
- 1
- 2
- 3
- 4
- 5
- 6
- 7
- 8
- 9
- 10

Please select the number (0= no pain, 10= pain as bad as you can imagine) that best describes your pain at its least in the last 24 hours.

- 0
- 1
- 2
- 3
- 4
- 5
- 6
- 7
- 8
- 9
- 10

Please select the number (0= no pain, 10= pain as bad as you can imagine) that best describes your pain on the average.

- 0
- 1
- 2
- 3
- 4
- 5
- 6
- 7
- 8
- 9
- 10

Please select the number (0= no pain, 10= pain as bad as you can imagine) that best describes how much pain you have right now.

- 0
- 1
- 2
- 3
- 4
- 5
- 6
- 7
- 8
- 9
- 10

Please select the number (0= does not interfere, 10= completely interferes) that best describes how, during the past 24 hours, pain has interfered with your: **General Activity**

- 0
- 1
- 2
- 3
- 4
- 5
- 6
- 7
- 8
- 9
- 10

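### The primary endpoint in mg is computed from counts per colour and format, with no product name or labelled strength recorded, so mg cannot be recovered where products in one cell differ in strength

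*Protocol*

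**What the plan says.** Section 7.1 makes the physician-selected regimen and its changes over time the primary endpoint, with the first component given as "1) average daily dose of THC and CBD (in mg"). Subject-selected dose is a secondary endpoint in the same units. Section 4.2 explains how mg is obtained: "the preprogrammed algorithm will calculate the intake amount of mgs of THC and CBD for all formulations".

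The inputs to that algorithm are in the regimen tables of Appendices 1, 2 and 3. Each row is a colour and each column a format: inhalations, mL of oil, sprays, low-potency capsules and edibles, and high-potency capsules. The entry is a daily count. The low-potency column asks the user to "report daily total number of low-potency capsules (i.e. 2.5 mg), number of chocolate bar squares, etc". The high-potency column states no strength. Rows are described by example, such as "Red (examples include Spectrum #1-4; Tweed Bakerstreet, Highlands, Houdstooth, Donegal; LBS Sunset"), and there is a row for "Spectrum Clear (or White") that takes mL of oil. The table has no field for the product actually used. A product name is requested only on the adverse event form.

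Figure 1 in section 4 gives content for dried flower (% by weight), oil (mg/mL) and soft gels (mg), mostly as ranges. The Blue soft gel entry, for example, reads "2.5 – 10) THC : (1.75-15) CBD".

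**The concern.** Apart from inhalation method and vaporizer temperature, which the form also asks for, a conversion based on this form can use only colour, format and count. If two products of different strength fall in the same cell, no fixed factor is right for both. A change from one to the other leaves the count, and so the calculated mg, unchanged.

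The primary endpoint includes change in mg over time, and a secondary objective is to describe product and dose adjustment. Section 4.1 says that subjects in Canada may change product freely. A strength change within a cell is therefore the kind of event the registry sets out to describe, and the form would miss it. A later analysis plan cannot repair this, because it cannot restore product identity that was never collected.

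**Working it through.** The protocol prints no conversion factor, so there is no stated figure to reproduce. The check has four parts.

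**1. Spread of content within a colour (Figure 1, maximum / minimum)**

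| Format | Colour, cannabinoid | Range | Ratio |
|---|---|---|---|
| Soft gel | Red THC | 2.5 to 10 mg | 10 / 2.5 = 4.0 |
| Soft gel | Blue THC | 2.5 to 10 mg | 10 / 2.5 = 4.0 |
| Soft gel | Blue CBD | 1.75 to 15 mg | 15 / 1.75 = 8.57 |
| Soft gel | Yellow CBD | 5 to 20 mg | 20 / 5 = 4.0 |
| Oil | Blue CBD | 12 to 15 mg/mL | 15 / 12 = 1.25 |
| Oil | Red THC, Blue THC, Yellow CBD | 26.3, 10, 20 mg/mL | 1.0 (single values) |
| Flower | narrowest, Red THC | 17 to 23% | 23 / 17 = 1.35 |
| Flower | widest, Green THC | 4 to 7% | 7 / 4 = 1.75 |

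If strength were ignored altogether, two Blue soft gels a day could mean 2 × 2.5 = 5 to 2 × 10 = 20 mg THC, and 2 × 1.75 = 3.5 to 2 × 15 = 30 mg CBD.

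**2. Effect of the low/high potency split**

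Strength is not ignored altogether, because low- and high-potency capsules have separate columns. Assume that low potency means exactly 2.5 mg THC for Red and Blue. The THC spread left in the high-potency cell then depends on its lowest strength, which is not stated:

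- lowest strength 5 mg: 10 / 5 = 2.0-fold
- lowest strength 7.5 mg: 10 / 7.5 = 1.33-fold
- lowest strength 10 mg: 10 / 10 = 1.0-fold

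For Blue CBD the remainder cannot be computed, because the protocol does not say how 1.75 to 15 mg divides between the two columns. For Yellow, the 2.5 mg label fits neither range in Figure 1 (<1 mg THC, 5 to 20 mg CBD). If all Yellow soft gels are entered as high potency, the whole 4-fold CBD range stays in one cell. If some are entered as low potency, the label does not describe them. Chocolate squares share the low-potency field and have no stated content, so even the unit of that count is ambiguous.

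**3. Form cells against Figure 1**

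| Column of the form | Cells that can be filled in | Without content in Figure 1 |
|---|---|---|
| Inhaled | 6 | 0 (% by weight only) |
| Oil | 5 | 2 (Green, Clear/White) |
| Spray | 6 | 6 |
| Low-potency capsule/edible | 4 | 1 (Green) |
| High-potency capsule | 4 | 1 (Green) |
| Total | 25 | 10 |

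**4. Inhaled products**

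The six inhaled cells take a number of inhalations. Figure 1 gives flower content by weight, and no mass per inhalation is stated, so a label percentage and a count do not give mg. Section 4.2 says first that the algorithm covers all formulations, and then says of inhaled products: "It is possible that these data may be calculated in retrospect (unlike other formulations that will allow for real time mg calculation"). These two statements need to be reconciled.

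**The case against.** The strongest reply has four parts.

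- **Unseen equations.** The algorithm exists, and each calculated field links to an equation. Neither the equations nor the figures above the regimen tables are reproduced, so the constants cannot be judged. This stands: one cannot say that the constants are wrong or absent. It does not answer the main point, since no equation can use a product identity that the form does not collect.
- **Upper bounds only.** A reader might infer that each capsule entry carries a 4-fold or 8.6-fold error. The documents do not support that. For example, the Red soft gel range of "2.5-10) THC : (<1) CBD" covers every strength of the colour, while the form splits capsules in two. Most other formats are much narrower, and a switch between formats or potency columns is recorded.
- **Figure 1 is an overview.** It is not presented as the algorithm's lookup table, and an open cell that nobody uses causes no error. This is fair. The 10 cells show a mismatch between form and figure; they do not amount to 10 wrong doses. Only the Red row names several products.
- **No claim of precision.** The primary objective is descriptive and the form labels the calculated dose as approximate. That lowers the stakes, but the degree of approximation is still not known, and it could be reduced at little cost.

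A reader might also infer that the errors distort comparisons between countries. No calculation shows this. Only the Canadian form is shown, and section 4 says that Germany has flower only, so the soft-gel ranges do not apply there.

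**Conclusion.** The concern holds in a limited form. The regimen form shown records neither product nor labelled strength, so where products in one cell differ in strength the true mg cannot be recovered from it, and a switch within the cell is not seen. This is clearest for ingested formats: capsules and chocolate squares share a field, the high-potency strength is not stated, and the low-potency label does not fit Yellow.

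The soft-gel spreads of 4-fold (THC for Red and Blue, CBD for Yellow) and 8.6-fold (CBD for Blue) are ceilings. For Red and Blue THC the remaining spread is 1.0- to 2.0-fold under the assumed high-potency strengths; for Blue CBD it cannot be computed. Three oil values carry no spread. It would go too far to say that the mg dose is undetermined in general.

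The conclusion assumes that the regimen tables are complete as printed and that some cells hold products of more than one strength, as the ranges in Figure 1 and the shared capsule/edible field suggest.

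**What to change.** - Add a product pick-list to the eCRF with labelled THC and CBD per unit: mg per capsule, mL, spray or square, and % for flower. Keep colour as a grouping for display.
- Give capsules and edibles separate fields.
- Compute ingested mg from the label of the product selected.
- Reconcile Figure 1 with the form for sprays, Green oil and capsules, Clear/White oil and chocolate, and resolve the Yellow low-potency label.
- For inhaled products, record the product and its labelled content, but report inhaled mg separately from ingested mg and as approximate. A pick-list does not supply mass per inhalation. Align the two statements in section 4.2 accordingly.

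The cost is slightly more entry work, part of it for subjects at home, and upkeep of the list as products change. Nothing about treatment changes.
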